- 3) Procedure for blood processing for RNA, DNA, and protein: 10mls of whole blood will be collected in each of the following tubes: PAXgene Blood DNA Tube, one PAXgene Blood RNA Tube, 2 Green-top-Heparin blood collection tubes for a total of 60 mls of whole blood. Tubes should be immediately inverted several times to prevent clotting. Blood will then be shipped on wet ice to processing lab at the Baltimore VA. Samples will be labeled with an identification number, date, and visit type. Upon arrival, Paxgene tubes will be frozen at -

70°C pending nucleic acid processing. RNA tubes will be stable up to 6 months post freeze. DNA tubes will be stable indefinitely. Heparinized collection tubes must be processed for protein immediately. To process whole blood for protein, tubes must be centrifuged at ~900g at room temperature for 15 mins. Serum will separate from cells and will be collected and stored at -70°C until protein processed. The red blood cells will then be lysed using Qiagen's QIAamp procedure which uses a hypotonic buffer for selective lysis of erythrocytes. The remaining leukocyte pellet will then be frozen at -70°C pending processing. To process protein, Agilent Technologies Human 14 Multiple Affinity Removal Spin Cartridges will be used.

DEXA scan

Participants will undergo a total body dual energy x-ray absorptiometry (DEXA) (Hologic QDR1000/W, software version 6.2OD; Waltham, MA) to assess fat free mass and fat mass according to standard GCRC protocols.

Intervention Protocol

TDPA group:

1) TDPA Exercise Component:

For the Tailored Diet and Physical Activity (TDPA) intervention group, the training protocol consists of a graduated walking program, with additional focus on specific balance exercises. During the 1.5 hour orientation period, the home balance exercises and walking program will be introduced and the appropriate level of balance challenge and walking intensity will be established.

The walking program will utilize the guide "The Exercise and Your Heart: A Guide to Physical Activity" program sponsored and developed by the National Heart, Lung and Blood Institute and the American Heart Association. Along with the walking program, the guide includes additional content such as Benefits and Barriers to physical activity (PA), Keys to Success, and Pacing Yourself. The guide will be supplemented with materials from the PBS America Walks website www.pbs.org/americawalking/index.html.

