The TDPA program includes a tailored behavior change component to facilitate the adoption of long-term PA behavior. The goal is to increase the intervention participants' PA levels and maintain those levels across time (12 months). TDPA participants receive 60 minutes of tailored lifestyle behavioral change instruction during the orientation period, followed by behavioral support via telephone calls **or email** weekly for the first three months (months 0-3), biweekly for 3 months (months 4-6), and monthly for the remaining 6 months (months 7-12) to reinforce behavioral strategies such as relapse prevention, goal setting, overcoming barriers (e.g. weather, increasing self-efficacy, and self-monitoring of PA. Monthly mailings throughout the 12 month intervention are used to reinforce and adapt the program as needed, as we have done in our pilot studies.

To promote an individualized (tailored) PA program and identify preferences for tailoring, participants will complete a questionnaire at baseline (See Appendix) that includes theoretical items noted to impact PA behavior. Findings support that older adults intend to perform PA if they: (perceive benefits of PA (outcome expectancies) and perceive confidence to perform PA in spite of barriers (self efficacy) (102) and confidence to walk (self-efficacy for walking).

Responses from the questionnaire will be used for behavioral counseling, telephone calls, **email** and mailings. A library of tailored messages and strategies has been developed for each combination of responses (e.g. low benefit/low self-efficacy, high barriers/low self-efficacy). Each participant's program will be tailored based on: 1) personal psychosocial determinants (self-efficacy, benefits, barriers); 2) PA preferences; 3) available community resources; and 4) health and environmental factors. Examples of the theory-based tailored behavior strategies are presented in the following table.

Example of Tailored Behavior Change Based on Assessment Data:

Behavior/Problem Examples	Goal of Intervention	Tailored Intervention (BC=Behavioral Counseling; TS=Tip Sheets; CR=Community Resources; RP=Relapse Prevention; TC=Telephone Call)

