In the TDPA group, the dietary protocol will be based on the Bouchard 3 day dietary instrument and will include individual tailored dietary instruction with the goal of reducing baseline weight by at least 7%. During the 2 hour orientation appointment, the nutritionist will perform a one-on-one dietary consult with the subject and establish a nutritional plan. The dietary consult will assess the individual participant's diet at enrollment and develop a specific plan for that individual (weight loss >7% baseline weight). This will include developing a calorie-restricted diet, addressing the distribution of energy yielding macronutrients, and will also develop a long term plan to improve the quality of the participant's diet so as to achieve a safe but consistent negative balance. For each individual participant, the basal metabolic rate and total energy expenditures will be determined based on PA assessment using Harris Benedict equations and criteria developed by the Food and Nutrition Board of the Institute of Medicine (103). Based on this information and BMI, the nutritionist will provide individual information on the calorie reduction to provide steady weight loss. The dietician may meet with the subject again one month after the initial consult and may also meet as needed with the subject during the 12 month intervention depending on the needs of the subject, compliance with the protocol, and the decision of the dietician and TDPA interventionist. The initial consultation session will be followed up with counseling 1 and 2 weeks after enrollment by the TDPA interventionist and then monthly 30 minute telephone **or email** assessments and behavioral counseling to promote

individual dietary goals. The dietician will meet with the subject, at the 6 month return visit and at the 12 month visit.

TDPA Intervention Summary

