This program consists of several components that have been shown to improve exercise compliance, and, in our preliminary data, to be feasible in physically impaired older adults. These include: personalized program emphasizing activities that are meaningful to or preferred by participants; consistent contact between the participants and research staff; and monitoring of activity levels by log, Actigraph (an accelerometer worn at the waist that measures physical activity). Participants will place PA goal sheets, Tip Sheets, exercise pictures and instructions, behavior change materials, and balance program information in a project-provided binder for reference at home.

Participants that are failing to meet their established dietary and PA goals as assessed by the TDPA interventionist during telephone interviews **or email** at 1, 2, or 3 months will be asked to meet face-to face with the assessor to re-establish dietary and PA goals.

Intervention-Protocol - SC group:

The SC group will be told following their DEXA appointment that they should reduce their baseline weight by 7% and exercise for at least 150 minutes/week. There will be no tailored, directed program. These participants will attend a total of 90 minutes of health education classes (no behavior change component) during the orientation period and receive general health related telephone calls **or emails** weekly during the first 3 months, biweekly during the next 3 months (months 4-6) and monthly for the remaining 6 months (months 7-12) and monthly health related mailings throughout the intervention (12 months). The time allocated to these health activities in the SC group is the same as the TDPA, in order to control for a possible attention and monitoring effect.

Data management

The technician utilizes a structured data entry system into a database with range checks on individual items and double keying to ensure accuracy. Data are entered into computers as per standard protocols. Data are cleaned and edited after being transported into a statistical software package. Protocols have been developed to handle missing or out of range values, documentation, file backup and archiving, and confidentiality procedures. Co-Investigator [name] will participate in the design of these protocols, choice of software platforms, computer data organization and structures, merging data sets, and data transport.

Independent Safety and Data Monitoring Committee (SDMC)

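### The equal-contact-time statement holds for the calls, mailings and exercise orientation but not for the TDPA nutrition component, so attention is only partly controlled

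*Combined protocol and SAP*

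**What the plan says.** Under the heading for the SC group's intervention, the plan says that "The time allocated to these health activities in the SC group is the same as the TDPA", so that attention and monitoring are controlled. SC is described as follows: "These participants will attend a total of 90 minutes of health education classes (no behavior change component) during the orientation period". SC also gets general health calls or emails (weekly in months 0-3, biweekly in months 4-6, monthly in months 7-12), monthly mailings, and advice of unstated length after the DEXA visit.

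The TDPA arm is described in three components:

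- **Exercise.** The walking and balance program is introduced as follows: "During the 1.5 hour orientation period". Calls or emails then follow the same calendar as in SC.
- **Behavioral.** "TDPA participants receive 60 minutes of tailored lifestyle behavioral change instruction during the orientation period", with support calls on that calendar and monthly mailings.
- **Nutrition.** "During the 2 hour orientation appointment, the nutritionist will perform a one-on-one dietary consult". Counseling follows at weeks 1 and 2, "and then monthly 30 minute telephone" or email assessments after that, and dietician meetings at the 6- and 12-month visits. Further dietician meetings are optional.

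The TDPA Intervention Summary adds face-to-face meetings for participants who miss their goals at 1, 2 or 3 months. Item 4 of the potential limitations says that the control arm's health education follow-up is there to match the added attention in the intervention arm.

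**The concern.** The SC contacts mirror the exercise and behavioral side of TDPA. Nothing listed for SC mirrors the nutrition side, yet the sentence claims equal time without that limit.

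This matters because the protocol itself treats contact as an active ingredient. Its section on components of effective PA interventions links more personal contact, and more intense contact, to larger effects. If TDPA participants also receive more contact, a TDPA-SC difference cannot be credited to tailoring with attention held equal. The exposure is greatest for self-reported CHAMPS activity. It is smaller, but not absent, for the 6MW, which is walked at a pace that the participant chooses.

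**Working it through.** **Inputs**

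- SC classes: 90 min = 1.5 h (SC group section).
- Scheduled calls or emails: about 13 weekly + 6 biweekly + 6 monthly = 25 in SC, and the same calendar in the TDPA exercise and behavioral components. Length is stated in neither arm.
- Mailings: 12 monthly in each arm.
- TDPA orientation: 1.5 h exercise, 1 h behavioral, 2 h nutrition appointment. The plan does not say whether these overlap.
- TDPA dietary follow-up: weeks 1 and 2 (untimed), then monthly contacts of 0.5 h. Twelve contacts if one falls in every month. I also take 10, for instance if the 6- and 12-month visits replace two of them (an assumption).
- Untimed and left out: week 1 and 2 counseling, dietician meetings, remedial meetings.

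**Step 1: reproduce the stated equality.** Exercise orientation minus SC classes: 1.5 − 1.5 = 0 h. Scheduled contacts: 25 − 25 = 0. Mailings: 12 − 12 = 0. For these components the statement is reproduced.

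**Step 2: add the remaining timed sessions.** Excess = O − 1.5 + 0.5 × n, where O is TDPA orientation time in hours and n the number of separate 30-minute dietary contacts. All entries are hours.

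| Reading of the orientation | O | Orientation only (n = 0) | 6 months (n = 6) | 12 months (n = 10) | 12 months (n = 12) |
|---|---|---|---|---|---|
| Everything inside the 2 h appointment | 2.0 | 0.5 | 3.5 | 5.5 | 6.5 |
| 2 h includes the 1.5 h; behavioral 1 h added | 3.0 | 1.5 | 4.5 | 6.5 | 7.5 |
| 1.5 h includes behavioral; 2 h added | 3.5 | 2.0 | 5.0 | 7.0 | 8.0 |
| All additive (1.5 + 1 + 2) | 4.5 | 3.0 | 6.0 | 8.0 | 9.0 |

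The first row is generous to the plan. Since 1.5 + 1 = 2.5 h exceeds 2 h, the behavioral hour has to overlap the exercise session.

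**Step 3: what would change the result.**

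- If every dietary contact is merged into an exercise or behavioral call, n = 0 and the timed excess is 0.5 to 3.0 h.
- Longer SC calls could offset the difference. Twelve dietary contacts are 6 h = 360 min, and 360 / 25 = 14.4 extra minutes on each SC call. The smallest orientation excess, 30 min, would need only 30 / 25 = 1.2 minutes per call. The documents describe no such lengthening.
- Counting the untimed dietary counseling and meetings would raise every figure.

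**Step 4: are the dietary contacts separate?** The rationale for the primary hypothesis lists dietician follow-up as one item and the PA program, with its own calls, as another. The study schedule ties the food record to nutrition calls, and the section on nutrition compliance has the dietician counsel from that record at each nutrition contact. Against this, the Nutrition Component gives the week 1 and 2 counseling to the TDPA interventionist, and the Intervention Summary has the interventionist assess dietary and PA goals together. The balance favors separate contacts but does not settle it.

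**The case against.** The strongest reply has four parts.

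1. **The hours are not fixed by the plan.** A reader might infer that the protocol's own sessions give TDPA 6.5 to 9 more hours. They do not. Six of those hours need twelve dietary contacts, all separate from the other calls, all equivalent to 30 minutes of live contact although email is allowed, and none offset by SC calls of unstated length. This part stands, and the figures have to be read as conditional.
2. **Much is matched.** A reader might infer that the trial is not attention-controlled. That is too strong, because call calendar, mailings, and exercise orientation against class time do correspond. The weekly TDPA activity logs are self-completed and mailed back, so they are not staff contact time. This also stands.
3. **The sentence may cover only the matched activities, or may itself set a rule that SC time be equalized.** On the first reading it is true but leaves the diet component's attention uncontrolled, so it does not achieve its stated purpose. On the second, the listed SC sessions do not carry the rule out. Either way the text needs clarifying.
4. **The consequence is limited.** The hypotheses already compare TDPA as a program with SC. Outcome assessors are blinded, the 6MW is given without verbal encouragement, and CHAMPS is corroborated by Actigraph. These points reduce the risk of biased assessment. They do not separate the effect of tailoring from that of extra contact on what participants actually do.

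**Conclusion.** The concern holds in a limited form. The equal-time statement is supported for the call schedule, the mailings, and exercise orientation against classes. It is not supported for the TDPA nutrition component or the remedial meetings, which have no listed SC counterpart. Attention is partly controlled.

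In timed sessions, TDPA exceeds SC by 0.5 to 3.0 h at orientation under every reading of the overlap. With separate 30-minute dietary contacts and SC calls no longer than TDPA calls, the excess is about 3.5 to 6 h by the 6-month primary endpoint (6 contacts) and about 5.5 to 9 h by 12 months (10 to 12 contacts). Merged contacts, email or longer SC calls would shrink it; the untimed counseling and meetings would enlarge it. The true difference in total minutes cannot be derived from the documents.

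What changes is the causal claim. A positive result would support the TDPA package, not tailoring with contact time held equal. Sample size, error rates and the analysis model are unaffected.

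**What to change.** 1. Reconcile the three TDPA component sections with the SC section: say whether the 1.5 h, 60 min and 2 h blocks overlap, whether the dietary contacts are separate from the exercise and behavioral calls, and how long calls are meant to last in each arm.
2. Limit the equal-time sentence, for example: *SC matches TDPA on the schedule of exercise and behavioral calls or emails, on monthly mailings, and on class time against exercise orientation; the TDPA nutrition contacts and remedial meetings have no SC match.* Align item 4 of the limitations with it.
3. Record contact minutes and mode (in person, telephone, email) per participant in both arms, and report them by arm to 6 and to 12 months.
4. State that a TDPA-SC difference is the effect of the whole TDPA package, including its extra contact, with attention only partly controlled.

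The cost is a small recording task and a narrower causal claim. The only log described is the TDPA participants' activity log, so a staff contact record may have to be set up. Neither the interventions nor the endpoints need to change.

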Sample size will be based on the previous data from our IGTN natural history study and relevant pilot data from our ongoing Rehab R&D-funded Merit Review T2DM exercise study. An assumption is that the IGTN study represents a more intense intervention than SC and that the difference between the TDPA and the SC will be at least as large as the difference between baseline and the 6 or 12 months endpoints of IGTN (see below). The table below uses the IGTN baseline-endpoint data to compute an adjusted standard deviation (i.e. the SD can be reduced by taking into account the contribution of each individual's baseline in explaining the overall variation). For the T2DM study, PA (from CHAMPS scores) is available at baseline (Mean \pm SD 1350.5 \pm 946.5) and at 10 weeks of a physical activity enhancement intervention for our pilot group (10 week delta=over 600). At present, we do not have sufficient 6 or 12 month data for PA in T2DM, but we anticipate that the initial PA benefit may be sustained. The expected sample size required is noted for two-sided alpha=0.05 and with power of 80%.

Study	Variable	SD of the outcome adjusted for baseline	Desired TDPA-SC difference	Effect size for adjusted outcome	Sample size per group
IGTN	6MW	97	50	0.51	64
IGTN	IENFD	2.2	1.0	0.45	53
T2DM	PA	1000	500	0.50	64

Thus, the sample size estimate needed for the primary hypothesis efficacy measure (6MW) will be 64 per group for a total of 128 needed in the study. In the T2DM CHAMPS PA data, using baseline information and assuming a delta of 500 and standard deviation of 1000, with 64 subjects per group we can detect an effect size of 0.5. Based on reliable data from the current IGTN study, we know that the actual 1 year dropout for enrolled subjects is 4%, so that the number of subjects to be enrolled is 133. We estimate a more liberal 10% dropout rate from

baseline to the 12 month endpoint, thereby requiring randomization at baseline of 142 in order to guarantee recruiting the necessary 128 participants.

The sample size estimate needed for the secondary hypothesis efficacy measure (IENFD) will be 53 per group for a total of 106 needed in the study. Using the 10% dropout rate from baseline to the 12 month endpoint, 117 would be required for randomization, well within the 142 planned to satisfy the requirements for 6MW noted above.

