This study will use a lifestyle intervention and it is not predicted from the current IGTN study that a standing independent SDMC will be required. If necessary, a plan for convening a SDMC is described in Human Studies (see Appendix).

General analytic plan

Comparability of treatment groups will be performed using the baseline demographic variables (i.e. age, gender, BMI) and relevant prognostic covariants (e.g., HbA1c, autonomic symptoms, and baseline values of primary endpoints). The demographic and prognostic values will be presented by treatment group as means and standard deviations for continuous variables, and analysis of variance will be used to compare the means of the two treatment groups, controlling for baseline. Baseline characteristics will be compared between the study groups. Standard two group comparison methods will be used, such as two sample t-tests for normally distributed variables. Measures of central tendency (means) and variability (standard deviations, ranges) will be estimated. Initial data analyses will allow us to explore the distributions of outcomes studied, may lead to transformation of the dependent variable, and may help identify outlying measures not detected earlier in the data cleaning process.

1) Model check and alternative analysis plans: Model fits will be checked for individual and systematic departures of the observed and fitted values using informal (e.g. inspection of residuals) and formal methods (e.g. based on score tests for extra parameters (104;105). The influence of individual outliers will be evaluated by comparing models with and without outlying values. Outcome variables will be transformed when we cannot fit a parametric model. In our

preliminary data, assumption of normality is reasonable for most outcome variables, including those which are log transformed. Non-parametric analyses e.g. Generalized Additive Models (GAM), (106), or Friedman two-way analysis of variance (105), will be utilized when we cannot fit a parametric model. Outcome measures will be adjusted for baseline by including baseline values as a covariate into the model. As another option, a baseline measure becomes another dependent variable in the repeated measures model and appropriate contrasts will be constructed to adjust for baseline. In computations, SAS PROC MIXED (107), SAS PROC GENMOD, and PROC GAM in SPLUS will be used.

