5) Strategies for multiple inferences: The analysis involves several hypotheses tests, thereby requiring a strategy to control the alpha level. We will give higher priority to the primary hypothesis so that the outcomes of tests of mechanism hypotheses will not be given the same strength of interpretation. Overall significance levels will be controlled using the probabilistic inequalities (e.g. Bonferroni or Sidak's methods), adjusted confidence limits (e.g. Tukey), methods based on resampling (109) or other appropriate multiple comparison adjustment methods (7).

Hypothesis testing plan

For the purposes of hypothesis testing, specific key primary and secondary variables, based on previous pilot data have been identified.

Endpoints	6 month	12 month
Primary	6 minute walk (6MW)	
Secondary	Physical activity (PA)	IENFD
Tertiary		6MW, PA

Primary Hypothesis (6MW at 6 months): Compared to IGR participants advised to follow the current standard care recommendations on diet and PA (Standard Care or "SC"), IGR participants undergoing TDPA enhancement program will show greater improvement in the 6 Minute Walk (6MW) at 6 months.

Secondary Hypothesis 1 (PA at 6 months): At 6 months and compared to SC, TDPA participants will show greater improvement in self-reported PA.

For the Primary Hypothesis and Secondary hypothesis 1 that address the 6-month 6MW and PA intervention effect, the goal is to determine whether there is a group (TDPA versus SC) difference in 6-month improvement. A regression model will be used to test these hypotheses

controlling for the minimization variables and baseline outcomes (BA=outcome at baseline; GEN=Gender; BMI=Body Mass Index, Age=Age, GRP=intervention group):
Outcome at 6 months= BA+GEN+BMI+AGE+GRP

Secondary Hypothesis 2 (IEFND at 12 months): At 12 months and compared to SC, TDPA participants will show better maintenance of IEFND.

A similar strategy will be used to test for the 12 month intervention effect.

Outcome at 12 months= BA+GEN+BMI+AGE+GRP

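### The Friedman fallback compares visits, not TDPA with SC, and should be replaced by a rank method that keeps the group term and baseline

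*Combined protocol and SAP*

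**What the plan says.** Item 1 of the General analytic plan (model check and alternative analyses) has two sentences with the same trigger. One is "Outcome variables will be transformed when we cannot fit a parametric model". The next gives two examples of non-parametric analyses, a generalized additive model (GAM) or "Friedman two-way analysis of variance (105), will be utilized when we cannot fit a parametric model". The item goes on to promise that outcomes will be adjusted for baseline, and on software it says "In computations, SAS PROC MIXED (107), SAS PROC GENMOD, and PROC GAM in SPLUS will be used". No procedure is named for Friedman.

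The Hypothesis testing plan defines what has to be tested. For 6MW and PA, "the goal is to determine whether there is a group (TDPA versus SC) difference in 6-month improvement", through the model "Outcome at 6 months= BA+GEN+BMI+AGE+GRP". IENFD at 12 months has the same right-hand side. The plan then identifies GRP as the key parameter in all of these models. For outcomes that are not normal, that section has its own list: inverse, log or power transformations, or a GLM with Poisson or gamma error.

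The plan does not say what the blocks and treatments of the Friedman test would be, or how the two fallback lists are ordered.

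**The concern.** Friedman ranks repeated conditions within a block. It suits a design in which every block receives every condition. Here the condition of interest is the arm, and each participant has only one. The natural blocks are participants and the natural conditions are visits, so the test would detect change over time shared by the whole sample. It would say nothing about TDPA against SC.

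Shared improvement is a realistic setting. The SC section tells controls to aim for 7% weight loss and 150 minutes of exercise a week. The natural history cohort, which had only general advice, improved its 6MW at 6 and 12 months. A Friedman result could then be read as an intervention effect when there is none, or could miss a real one.

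**Working it through.** The plan gives no figure for this fallback, so there is none to reproduce. The check is one of structure, followed by a simulation.

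**Structure, three visits (6MW, PA).** Within each participant the ranks are 1, 2, 3 and sum to 6 whatever the arm. GRP is constant within the block, so it cannot enter the statistic. Nor can baseline (which becomes one of the ranked visits), gender, BMI or age.

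**Structure, two visits (IENFD).** Table 5 shows IENFD at baseline and 12 months only. With two visits Friedman reduces to a sign test of whether values rose or fell, pooled over arms.

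**Other blocks.** Minimization strata could serve as blocks with arms as conditions. The listed factors give 4 age × 2 gender × 3 BMI = 24 cells for 128 participants, about 5.3 per cell, so a modified test or cell summaries would be needed. The plan specifies nothing of this kind.

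**Simulation inputs.** From the sample size table for 6MW: adjusted SD 97, difference 50, 64 per group, two-sided 0.05. Assumed, not in the documents: baseline to follow-up correlation ρ = 0.5, complete data, the same effect at 6 and 12 months, and follow-up errors independent given baseline. Gender, BMI and age were left out.

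Total SD = 97/√(1 − 0.5²) = 112.0. Baseline b is normal with that SD. Each follow-up is 0.5·b + error (SD 97) + the arm's mean change. Skewed errors are centred exponential with SD 97. There were 1,000 runs per row. Monte Carlo standard errors are about √(0.05 × 0.95/1000) = 0.7 points near 5% and √(0.82 × 0.18/1000) = 1.2 points near 82%.

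**Check on the simulation.** Expected power for the arm contrast is Φ(50/(97·√(2/64)) − 1.96) = Φ(2.916 − 1.96) = Φ(0.956) = 0.83. ANCOVA gave 82.0% to 83.7%, as it should.

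**Results, % of trials rejecting:**

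| Errors | SC change | TDPA change | Friedman | ANCOVA | GAM with GRP | Rank ANCOVA |
|---|---|---|---|---|---|---|
| Normal | 0 | 0 | 5.5 | 4.9 | 5.0 | 4.7 |
| Normal | +50 | +50 | 99.4 | 4.0 | 4.1 | 4.0 |
| Normal | 0 | +50 | 58.6 | 83.7 | 82.7 | 81.1 |
| Normal | −25 | +25 | 5.8 | 82.0 | 81.7 | 79.7 |
| Skewed | 0 | 0 | 51.0 | 4.9 | 4.9 | 5.6 |
| Skewed | +50 | +50 | 94.7 | 4.5 | 5.8 | 5.2 |
| Skewed | 0 | +50 | 10.4 | 83.7 | 82.9 | 94.2 |
| Skewed | −25 | +25 | 38.9 | 82.6 | 81.8 | 95.0 |

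Friedman follows the visit pattern and ignores the arm contrast. Its 51.0% in the fifth row arises because the simulated baseline is normal and the follow-ups are skewed, so the visits differ in shape although no mean changed. The rank ANCOVA here regressed the ranked outcome on ranked baseline and GRP. Quade's version does this in two steps and was not simulated separately.

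**Sensitivity.** A second simulation, with 2,000 trials, 128 participants, correlation 0.6 and total SD 97/√(1 − 0.36) = 121, had no arm difference. Friedman rejected in 5.2%, 25.8%, 63.0% and 99.9% for shared gains of 0, 15, 25 and 50.

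**GAM.** It carries GRP as an ordinary term and behaved like ANCOVA throughout. With skewed errors its power stayed at 81.8% to 82.9%, against 94.2% to 95.0% for rank ANCOVA. It relaxes the shape of the covariate effects, not the error distribution, so it does not by itself deal with skew.

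**The case against.** The best defence is that the plan never commits to Friedman for any endpoint. It is one of two examples, in general model-checking text, for use only if no parametric model can be fitted. The section that governs the hypotheses deals with non-normal outcomes by transformation or GLM, and both keep GRP. A within-person rank test would also be a legitimate check of the time effect that the plan lists separately. All of this stands, and it limits the point to the case where Friedman is used as the arm test. It does not rescue Friedman in that case: the sentence states no narrower purpose, and the method cannot serve the hypotheses it would be called on to test.

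A reader might infer that the GAM option has the same fault. It does not, as the table shows.

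A reader might also infer that PA is bound to reach this fallback, since baseline CHAMPS has mean 1350.5 and SD 946.5, a ratio of 0.70. That describes the raw baseline distribution, not residuals after adjustment, and a positive outcome with that spread is an ordinary case for a log transformation or gamma GLM. Item 1 also reports that normality is reasonable for most outcomes, some of them after log transformation.

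Finally, the plan says early data exploration "may lead to transformation of the dependent variable". A reader might infer that the scale will be chosen with the arms visible. The documents do not say so. They simply leave blinding of that choice unstated.

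**Conclusion.** The point holds for Friedman alone. With participants as blocks it cannot test TDPA against SC and cannot carry the promised covariates; that follows from the design and needs no assumption. The size of the possible error rests on the assumptions above: with equal arms both gaining 50, 99.4% rejection against 4.0% for ANCOVA; with a true difference of 50 in opposite directions, 5.8% against 82.0%. The simulations are scaled to 6MW and cover three visits, so they do not put a figure on IENFD or PA.

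These rates should not be read as the trial's error rate. They apply only if Friedman is chosen for a between-arm hypothesis, and the other listed routes avoid the problem. The change is worth making because the plan names an unsuitable method and a suitable one costs almost nothing.

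**What to change.** In item 1 of the General analytic plan, delete Friedman as a fallback for the between-arm hypotheses. Replace it with a Quade rank ANCOVA of GRP, adjusted for baseline, gender, BMI and age.

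State one order that covers both item 1 and the Hypothesis testing plan:

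1. The stated ANCOVA.
2. If its residuals are unsuitable, a transformation or GLM chosen on data pooled over arms and blinded to allocation.
3. If that fails, the rank ANCOVA.

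If a GAM is kept, say that it is for non-linear covariate effects and includes GRP.

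The cost is a few lines of text and little programming. The drawback is that rank ANCOVA gives a test, not an effect in original units, so the ANCOVA difference should still be reported beside it. It also loses a little power with normal errors: 79.7% against 82.0% under the assumed correlation of 0.5.
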